Better outcomes on social disability and hopelessness can be obtained from a more targeted intervention specifically focussed on improving social disability amongst those who have low functioning. We have developed a multisystemic form of CBT which targets social disability and have published a successful MRC trial platform study carried out amongst a group of young people who had established chronic and severe social disability problems some years after first episode psychosis. This trial demonstrated gains in structured activity and hope as well as reductions in symptoms (Fowler, et al., 2009). Clear indications of health economic benefits were also demonstrated (Barton, et al., 2009) although the trial was small and there was a large level of uncertainty associated with these estimates. We have subsequently applied this type of approach in clinical practice widening our selection criteria to include all young people presenting with severe and complex mental health problems at risk of social disability, drawing from our experience with EDIE 2 and this has been highlighted as an example of good practice (Joint Working at the Interface, 2011). We are now ready to undertake the feasibility phase of a substantive trial, which will be the first to specifically aims to address functional disability problems amongst the high risk population.

3. Research Methods

Design: The study will be a single blind, randomised controlled trial comprising of a 9 month intervention and 6 month follow up period involving 50 treatment cases and 50 controls in two centres. The study will constitute the feasibility phase undertaken in preparation for a large multicentre trial. A qualitative sub-study will be embedded within the pilot trial to evaluate the intervention from the subjective perspectives of patients themselves. Depending on data quality and recruitment the data will either be used as an external pilot or as the internal feasibility phase of a substantive trial. The NIHR accredited Norfolk Clinical Trials Unit advised on the development of the protocol and will provide ongoing expertise during the conduct of the study.

Setting: The intervention will be conducted in secondary mental health care settings, by therapists based in outpatient youth mental health early detection and early intervention services in mental health trusts in East Anglia (Norfolk and Suffolk) and Manchester.

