Target population: Young people aged between 16-25 presenting with persisting signs of social disability operationally defined as engaged in less than 30 hours structured activity per week and who are presenting to youth services in East Anglia and Manchester. They will also be presenting with either a). Attenuated symptoms of psychosis which meet criteria for an at risk mental state, or b). less severe attenuated psychotic symptoms and the presence of severe and complex mental health problems operationally defined by a score of less than 50 on the Global Assessment of Functioning (GAF) score. All potential referrals will be screened first with GAF

score, then activity levels will be checked by the Time Use Survey and symptoms assessed by the Comprehensive Assessment of At Risk Mental States (CAARMS).

Project timetable: The study will take place over 2.5 years (30 months). This involves a 15 month recruitment period in which we can realistically expect a rate of 3-4 participants randomised per month in each site. Given this rate of recruitment, we can expect to recruit to target to meet the 50 participants required from each site. Each participant will have a 9 month intervention and six month follow up. Recruitment will be monitored continuously via an independent DMEC.

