We will not be asking referrers to withhold any treatment. We will provide referrers with a best practice manual which gives guidance on providing optimal standard treatment for this type of case. Treatment as usual for this population should involve provision of short term individual and family psychological therapies available in IAPT and Child and Adolescent Mental health services and medication according to disorder specific protocols. Standard psychiatric care, psychological and vocational interventions from a variety of agencies will also be available to both treatment and control arms. All service contacts will be monitored during the trial duration. In addition our assessments will identify any risks to self or others and this will be communicated to the referring clinicians.

Anticipated problems with compliance: We are aware that young people with severe and complex mental health problems who are socially withdrawn with low activity levels often present challenges to clinical services, not least, that they may disengage from treatment. Despite this, our clinical experience with this type of

patient group is good. In our trial platform we achieved follow up data from over 90% of eligible clients on constructive economic activity (work, education) assessed by telephone and over 80 % from face to face interview assessments and we are confident in achieving similar levels of outcome with this participant group. Importantly the primary outcome assessment is Time Use and a useful estimate of time in constructive economic activity (work, education, voluntary work) can be assessed by telephone contact and triangulated by case worker report. All who enter the trial will have given permission to be contacted in this way. Similarly both our intervention and our assessment procedures are designed to be flexible and work in an outreach way to deliver the intervention and conduct assessments wherever is suitable for the participant. We have developed extensive experience over many years in managing such procedures in ways which are welcomed by young people with severe and complex mental health problems, safe for assessors and therapists and result in good levels of outcome.

Training and delivery

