The main measure of outcome in the economic analysis will be the EQ-5D (Brooks et al, 2006) (a generic measure of quality of life) which will be assessed at pre- and post-intervention. Secondary cost effectiveness from an NHS perspective will use three outcome measures: improvement in activity (Time Use), improvement

in symptoms (CAARMS) and improvement in quality of life (QALYs). An economic model will be constructed in order to estimate both the mean incremental cost and mean incremental effect of multisystemic social recovery CBT compared to treatment as usual. If one of these options were shown to be less costly and more effective than the other then this would suggest that it 'dominates' the other, and represents a cost-effective use of scarce resources. Alternatively, the mean incremental cost-effectiveness ratio associated with multisystemic social recovery CBT will be estimated and assessed in relation to a range of cost-effectiveness thresholds. The associated level of uncertainty will also be characterised by estimating the cost-effectiveness acceptability curve (showing the probability of the intervention being cost-effective at various levels of willingness to pay for health benefits). Sensitivity analysis will also be undertaken to assess the robustness of conclusions to changes in key assumptions. The above stated analysis would be undertaken in each of the above study designs though if an internal feasibility study/external pilot were to be conducted these would be considered only a preliminary analysis and would need to be treated with caution, compared to that of a full trial.

10. Proposed outcome measures

Primary Outcome: Hours per week engaged in constructive economic and social activity. This assessment is derived from the Office of National Statistics Time Use Survey interview (Short, 2006; Lader, Short, Gershuny 2006). It assesses hours spent in a range of activities and was successfully used as the primary outcome in our MRC trial platform study (Fowler et al, 2009). Further details are provided in the appendix below.

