Secondary outcomes: A well established mental state assessment will be used to assess levels of attenuated psychotic symptoms and associated psychopathology by interview (Clinical Assessment of At Risk Mental States (CAARMS). (Yung, Phillips, et al., 2006). In order to provide information on the difficulties experienced by participants in the study, the Structured Clinical Interview for DSM-IV (SCID; Spitzer et al, 1992) will be included at baseline and follow-up assessments. Emotional disturbance will also be assessed by brief self report questionnaires using the Social Interaction Anxiety Scale (SIAS; Mattick & Clarke, 1989) and Beck Depression Inventory-II (BDI-II; Beck, Steer, & Brown, 1996).

Health Economic outcomes: The main purpose is to monitor levels of resource use and quality of life, with a view to inform the decision as to how costs and benefits would be measured as part of any future more definitive study. A preliminary within trial cost-effectiveness analysis will also be undertaken. In line with guidance by the National Institute of Health and Clinical Excellence (NICE) (NICE, 2008) costs will be calculated from the perspective of the NHS and personal social services (PSS) using a modified version of the Client Service Receipt Inventory (CSRI; Thornicroft et al, 2006) and the Time Use Survey (Short, 2006). Quality of life will be assessed via the EQ-5D (Brooks, 1996) at pre and post intervention.

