Assessments of moderation and mediation: Cognitive function and motivational factors are likely to play a key role in mediating the effect of therapy on outcomes. The assessments will include a brief battery of self report questionnaires which will allow key tests of mediation hypotheses to confirm or reject the role of such factors. These include the Beck Hopelessness Scale (BHS; Beck & Steer, 1988); Schedules of personal meaning and hope (Snyder et al, 1991); Schizotypal Symptoms Inventory (SSI; Hodgekins et al, In Press); Brief Core Schema Scales (BCSS; Fowler et al, 2006) and Experiential Avoidance (Hayes et al, 2004). A short neuropsychological assessment comprising the Logical Memory I subtest of the Wechsler Memory Scale, Third Edition and the Controlled Oral Word Association Test (COWAT; Benton, Hamsher and Sivan, 1994), will confirm or reject the role of cognitive function in mediating effects on therapy. Additionally, two self-reports, the Alcohol Use Disorders Identification Test (AUDIT; WHO, 1989) and Drug Use Disorders Identification Test (DUDIT; Berman et al., 2002) will measure levels of harmful drug and alcohol use and allow hypotheses regarding the effect of such use on outcome to be tested.

Participants will, if they wish, be provided with a brief report of each assessment (baseline, 9 month follow up and 15 month follow up). The report will take the form of a letter addressed to the participant which summarises the outcome of the key assessment measures. The participant will be provided with copies of the report which they will be encouraged to share with other professionals involved in their care if they wish to do so.

11. Qualitative sub study

The qualitative sub-study aims to inform the objectives of the pilot RCT in preparing for a large scale randomised controlled trial, utilising a qualitative, service user perspective. The qualitative study will be split into 2 phases. Phase 1 will assess the feasibility of trail participation from a qualitative perspective, and phase 2 will seek to gain more in-depth understanding of participant's experiences at follow up.

Phase 1 qualitative sub-study:

The objectives of the qualitative sub-study are:

- 1. To explore in-depth with the qualitative sub-sample issues of recruitment and retention, focusing specifically on individual experiences of participating in the pilot RCT.

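### EQ-5D is scheduled only before and after therapy, so the last 6 of 15 months have no utility measurement, and no common horizon for costs and QALYs is stated

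*Protocol*

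**What the plan says.** Section 9 (Economic evaluation) of the Protocol plans a preliminary within-trial cost-effectiveness analysis with an incremental ratio and an acceptability curve. It states: "The main measure of outcome in the economic analysis will be the EQ-5D". The instrument's timing is given as "which will be assessed at pre- and post-intervention", and QALYs are named among the effectiveness measures. Section 10 (Health Economic outcomes) repeats the pre/post timing.

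Section 3 describes a design "comprising of a 9 month intervention and 6 month follow up period", and its project timetable confirms this for every participant: "Each participant will have a 9 month intervention and six month follow up". Section 10 gives the assessments as "baseline, 9 month follow up and 15 month follow up". On resource use, section 4 (Control) says: "All service contacts will be monitored during the trial duration".

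No section places the EQ-5D at 15 months, and none states the period over which costs and QALYs are to be compared.

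**The concern.** The main economic outcome appears to stop at the end of therapy, although the participant is seen again six months later and service contacts are still being monitored. QALYs depend on utility over time, so a period without an end measurement cannot contribute observed QALYs.

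This leaves the analyst two options. One is a 0–9 month horizon for both costs and QALYs. It is consistent, but it leaves out service use in follow-up. It also sets the whole cost of therapy, which is delivered inside the 9-month window, against QALYs accrued only to month 9. The other is a 15-month horizon, which needs an assumption about utility in months 9 to 15. Section 9 mentions an economic model but gives no such assumption.

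Two further consequences bear on the purpose of the pilot. Section 9 says the economic work is meant to inform how costs and benefits are measured in a definitive study, yet completion and variability of the EQ-5D at 15 months would not be tested. Section 7 expects these participants to form between a third and a half of a substantive trial if they are carried forward. They would then lack 15-month utilities, and a visit already past cannot be repeated. An analysis plan can choose a horizon, but it cannot supply data that were not collected.

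**Working it through.** **Inputs from the Protocol**
- Intervention 9 months, follow-up 6 months (section 3).
- Assessments at 0, 9 and 15 months (section 10).
- EQ-5D pre- and post-intervention (sections 9 and 10), read as 0 and 9 months.

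**Assumptions, not in the Protocol**
- d is the EQ-5D difference between arms at 9 months. No value is given; 0.05 is used below only as an illustration.
- The difference is zero at baseline and rises linearly to d at 9 months.
- It then moves linearly to d15 at 15 months.

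**Step 1: follow-up length.** 9 + 6 = 15 months, which agrees with the 15-month assessment. Share without a utility endpoint: 6/15 = 40%.

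**Step 2: QALY difference to month 9** (area under the difference curve, trapezoid rule)

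0.5 × d × 9/12 = 0.375d

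**Step 3: QALY difference to month 15**

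0.375d + 0.5 × (d + d15) × 6/12 = 0.625d + 0.25 × d15

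| After month 9 | d15 | QALY difference to month 15 | Observed by month 9 | With d = 0.05 (QALYs to month 9 vs 15) |
|---|---|---|---|---|
| Fades to zero | 0 | 0.625d | 0.375/0.625 = 60% | 0.019 vs 0.031 |
| Halves | d/2 | 0.75d | 0.375/0.75 = 50% | 0.019 vs 0.038 |
| Fully held | d | 0.875d | 0.375/0.875 = 43% | 0.019 vs 0.044 |

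The percentages do not depend on d. They do depend on the assumed shape. If the difference kept growing after month 9, less than 43% would be observed; if it reversed sign by month 15, more than 60% would be.

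**Step 4: the cost side.** The ratio over a horizon T is ΔC(T)/ΔQ(T), where ΔC is the incremental cost and ΔQ the QALY difference. The steps above give ΔQ(9)/ΔQ(15) under assumptions. The change in the ratio also needs ΔC(15) − ΔC(9), the incremental cost in months 9 to 15, and the Protocol gives nothing from which to derive it.

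**Step 5: how many could reach month 15.** Recruitment starts in month 4 (section 13) and lasts 15 months (section 3), so it ends in month 4 + 15 − 1 = 18. The last entrant's 15-month visit falls in month 18 + 15 = 33, but data collection finishes at month 30 (section 13). Entrants in months 16 to 18 could not reach it. With even accrual (assumed) that is 3/15 = 20%.

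**The case against.** **A mismatch between costs and QALYs is not stated.** A reader might infer that 15 months of cost will be set against 9 months of QALYs. The Protocol does not say so. The sentence in section 4 describes monitoring of service contacts in both arms and is not an economic horizon. Sections 9 and 10 give no time points for the service receipt inventory. A 0–9 month horizon for both sides fits the text, and the choice of horizon may properly be made in an analysis plan. This objection stands: the point is the missing measurement and the options it closes, not an announced error.

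**The size of any bias cannot be fixed.** A reader might turn the 60% and 43% into a cost per QALY overstated 1.7-fold (1/0.60) or 2.3-fold (1/0.43), and call the analysis biased against the therapy. Those multiples require the gain to persist and the incremental cost to be the same at 9 and 15 months. Section 6 says the benefits are yet to be demonstrated, and costs after month 9 could differ between arms in either direction. This objection also stands.

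**The analysis carries little weight.** It is labelled preliminary and to be read cautiously, and no progression criterion in section 1 or Appendix a uses cost-effectiveness. That lowers the severity. It does not answer the point about learning how to measure benefit for the definitive trial.

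**The timetable limits the remedy.** By Step 5, some late entrants would have no 15-month visit before month 30. This stands as a limit on the fix, but most entrants on that schedule would still be seen.

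**The wording could be looser than it looks.** Post-intervention might be meant to cover both later visits. This is the less natural reading, because section 10 places the diagnostic interview at baseline and follow-up assessments, in different words from those used for the EQ-5D. If it was intended, one sentence settles it.

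**Conclusion.** The point holds as a gap in data collection. On the natural reading of sections 9 and 10, the main economic outcome has no measurement in the last 6 of 15 months (40%), although an assessment is already planned at month 15, and the Protocol states no common horizon for costs and QALYs.

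If a difference rises linearly to month 9 and then persists in part or in full, about 60% (linear fade to zero) to 43% (fully held) of the 15-month QALY difference would be observed. These shares rest on the assumed shape and on no Protocol figure for the effect. Neither the size nor the direction of any distortion in the cost-effectiveness ratio can be derived from the Protocol.

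Severity is low to moderate. The economic analysis is preliminary and does not drive progression, but utilities not collected cannot be recovered later, and these participants may be carried into a definitive trial.

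**What to change.** Add the EQ-5D to the existing 15-month assessment in sections 9 and 10, and name the months in place of pre and post. State one horizon over which both costs and QALYs are calculated. Treat recruits who cannot reach month 15 before data collection ends at month 30 as administratively censored for costs and QALYs alike, and report their number. Report EQ-5D completion at 15 months as a feasibility result.

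If the EQ-5D is not added, state that both costs and QALYs are limited to 0–9 months and that later service use is described only.

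The cost is one short questionnaire at a visit already planned, a little more burden for participants, and one amendment line. The change does not give complete 15-month data, because of the late recruits.

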Allocation to groups: Following pre trial assessments consenting participants will be randomised to study arms stratified by age (16-19, 20-25); severity of social disability (Not in Education, Employment and Training or not) and meeting symptomatic criteria for an At Risk Mental State or not. Both groups will receive standard treatments as applicable. A remote, randomisation service will assign allocation to groups coordinated by the Norfolk Clinical Trials Unit.

Blinding: We will not be able to blind participants to treatment group. We will blind outcome assessors to group. To do so, following allocation to the treatment or control arm, all participants in the study, their care coordinator and the service user's clinical team will be asked not to reveal the group to which the participants were randomised to their assessor. Interview participants will also be asked at the beginning of each assessment interview not to disclose the group to which the individual was allocated. Outside the assessments, outcome assessors will be shielded from discussion of participants in study forums where the possibility of determining the allocation group of the participants could be determined. Qualitative interviews will be carried out by a researcher from another service or a university researcher independent of the clinical team. With the assistance of the Norfolk CTU we will use a system of web based data entry to ensure that assessors will not have access to information in the data base that would reveal the allocation group. To test the success of blinding we will ask the assessor to guess the allocation group for each participant at the end of each assessment.

Training of trial raters: The trial research assistants will be trained in the use of all measures by members of the team. Joint ratings with one another and with members of the team supervising them will be used to establish reliability.

4. Planned interventions

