- 2. To understand, from the participant's perspective, the level of involvement required and engagement with study tools and measures to date.
- 3. To analyse key variables of participants recruited to the pilot RCT to enable a detailed sampling frame to be established for phase 2 of the qualitative sub-study, and to inform sampling for the larger RCT.

Sampling: Initially, convenience sampling will proceed, recruiting to the qualitative sub-study all those consenting to be involved in the trial at baseline. Qualitative interviews will be undertaken between 1 and 3 months post-trial recruitment, in order to maximise recall of trial procedures around recruitment. Approximately 12 phase 1 qualitative interviews will be undertaken (6 from each randomised group).

Interviews: RAs will be trained and supported in qualitative interview techniques so as to elicit detailed data about the experience of recruitment, consent, and experiences of the study measures, tools and intervention, if appropriate. It is anticipated that interviews will last for no more than 60 minutes. All interviews will be audio recorded and transcribed verbatim.

Analysis: A broad thematic analysis will be undertaken in order that descriptive data from a service user perspective will be able to inform development of a larger RCT. Analysis will also describe characteristics of and differences between interviewees to enable purposive sampling for phase 2 of the qualitative sub-study, and to inform sample frame development for the larger RCT. Qualitative findings, in summary thematic form, will be utilised to contextualise and inform the pilot RCT aims of exploring recruitment, retention and acceptability of the study intervention.

Phase 2 qualitative sub-study:

This phase of the qualitative sub-study will seek to understand the narrative histories of participants, and the perspectives of users on their own subjective evaluation of their personal recovery including hopelessness, perceptions of stigma, and interpersonal functioning. The objectives of phase 2 are:

- 1. To explore the narrative experiences of young peoples' psychological difficulties as they understand them.
- 2. To understand young peoples' perceptions of their history of involvement with services.
- 3. To understand perceptions of treatments received as part of the research study and what impact this may not or not have made.
- 4. To explore hopes and fears for the future.

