Sampling: A sampling frame will be established to purposively sample participants with particular characteristics, in order that maximum variation across the study sample is achieved. Key constituencies of the sampling frame are likely to include randomised group, age, symptoms (i.e. severity), family background and previous history, gender and ethnicity. We will also attempt to ensure that the most vulnerable young people are recruited, including looked after children and those not in education or employment (NEET). This will ensure that a wide range of views and experiences are captured in phase 2 of the qualitative study. It is estimated that 16 study participants will be recruited for the qualitative sub-study, approximately 8 participants per randomised group.

Participants agreeing to take part in this further in-depth interview will sign a separate consent form, and will be interviewed at trial follow up (9 months)

Interviews: Qualitative interview guides will focus on key topics, but be flexible in allowing participants to explore their experiences in an open ended narrative manner that is meaningful to them, within the context of their own mental health experiences. Particular efforts will be made to attempt to elicit in-depth narrative accounts for detailed analysis.

Analysis: An Interpretative Phenomenological Analysis (IPA) approach to analysis (Smith et al, 1999. This approach will allow individual backgrounds to be analysed as a context to experiences. All interview data will be audio recorded and transcribed in full, using digital transcription software in order that nuances of speech are captured. Data will then be analysed line by line and thematically coded for meaning, aided by the computer

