Prior to start of the study: Preparations to be made before the beginning of the study will be a) obtaining ethics and research governance approvals (b) publicising the study to senior managers, clinicians and service users in the sites participating in the study (c) recruiting the first three members of staff beginning with the trial manager who will participate in the recruitment of other staff. (d) trial therapists will be identified before the start of the study and attend a series of pre study workshops discussing client information and undertaking their own pilot cases using the therapy manual.

The first 3 months (study set up period): The study will begin when the senior RAs are recruited in each centre. The process of publicising the study will continue. Therapy procedures and the procedures for optimal

treatment as usual will be finalised. Training will be provided for therapists in delivering the intervention. Training will be provided for the RAs in undertaking assessments.

Pilot study recruitment (Months 4 to 9): In month 4 recruitment to the pilot study will begin in teams in Norfolk and Manchester. Randomisation will follow gaining informed consent and an initial interview. Recruitment will continue for 6 months and patients will be followed up initially at 3 months.

Pilot study follow up assessments (months 7 to 12): Participants in the pilot study will initially be assessed at 3 months. At this point we will assess the feasibility of proceeding to a full trial, based on recruitment at this period. Pilot study follow up assessments will end in month 12(?15). Qualitative interviews will be undertaken at baseline and at three months.

Decision making and preliminary pilot study write up: (months 12 to 18): In months 13 and 14 we will consult the DMC as described above in order to decide whether to regard the data collected as an internal pilot and proceed to a full trial application or to set aside the data and change the protocol and write the preliminary pilot phase up as an external pilot. We will present to the HTA data on recruitment and retention in the pilot phase in order to obtain ratification of the decision and if necessary guidance. If the decision is not to proceed to a full trial we will make alterations to the inclusion criteria and changes to the protocol suggested by the preliminary pilot phase and continue recruiting to the study from the above 3 month stage reviewing again in between months 24 and 30.

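### Section 11 has the research assistants, who are the blinded raters, conduct the Phase 1 qualitative interviews; this conflicts with Section 3, and neither section bars an interviewer from later rating the same participant

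*Protocol*

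**What the plan says.** Section 3 (Research Methods) describes a single-blind trial in which participants know their arm. The protection it offers is on the assessor's side: "We will blind outcome assessors to group". Outside the assessments, "outcome assessors will be shielded from discussion of participants in study forums" where allocation might become apparent. The same Blinding paragraph has its own rule for the sub-study: "Qualitative interviews will be carried out by a researcher from another service or a university researcher independent of the clinical team".

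The next paragraph, on the training of trial raters, shows who the raters are: "The trial research assistants will be trained in the use of all measures by members of the team". Section 13 (Project timetable and milestones) agrees, for the set-up period: "Training will be provided for the RAs in undertaking assessments".

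Section 11 (Qualitative sub study), Phase 1, assigns the interviews differently: "RAs will be trained and supported in qualitative interview techniques so as to elicit detailed data". The topics include "experiences of the study measures, tools and intervention, if appropriate". About 12 interviews are planned, 6 from each randomised group, between 1 and 3 months after recruitment. Section 11 does not repeat the Section 3 rule on who interviews.

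Phase 2 interviews, about 16 at the 9-month follow-up, ask about treatments received. Section 11 names no interviewer for them.

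**The concern.** The staff who must not learn the allocation are the staff assigned to ask participants about the therapy. At an outcome assessment, participants are asked not to disclose their group; the Phase 1 interview invites them to talk about it. The qualifier that the intervention is covered where appropriate does not help. The interviewer must know the arm to decide whether the questions apply, or will learn it from the answers.

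The primary outcome is hours per week of activity, obtained by an interviewer through the Time Use Survey, and attenuated psychotic symptoms are also rated by interview (Section 10). With participants unblinded, assessor blinding is a central safeguard against measurement bias. The data may also be carried into a substantive trial if the progression criteria are met (Section 1 and Appendix a), so a rating made with knowledge of the arm could outlast the pilot. Lost blinding cannot be restored afterwards.

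**Working it through.** The protocol gives no figure on this point, so the check is mainly a comparison of its statements, followed by a simple calculation of size.

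**Step 1. Are the raters and the Phase 1 interviewers the same staff group?** Section 3 equates trial raters with trial research assistants, and Section 13 has RAs trained to undertake assessments. Section 11 has RAs trained to conduct the Phase 1 interviews. Yes, as a group.

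**Step 2. Does Section 3 assign the interviews elsewhere?** Yes: to a researcher from another service, or to a university researcher independent of the clinical team. Section 11 says only RAs, with no such restriction.

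**Step 3. Would Section 3's condition protect the ratings if it were followed?** Not by itself. It requires independence from the clinical team. A university-employed RA could meet that condition and still rate outcomes.

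**Step 4. Does the interview come before the ratings?**
- Phase 1 interview: 1 to 3 months after recruitment (Section 11).
- Main follow-up assessments: 9 and 15 months (Section 10). Both come later.
- Early assessment: 3 months (Section 13). It falls after the interview or around the same time, so it is possibly exposed.

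**Step 5. Is an interviewer barred from later rating the same participant?** No section says so, and none says that recordings or transcripts are kept from raters. Nor does any section say that an interviewer will rate the same participant.

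**Step 6. Size.**

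Inputs from the protocol:
- 12 Phase 1 interviews, 6 per arm (Section 11)
- 100 participants, 50 per arm (Section 7)
- minimum clinically significant gain of 4 hours (Section 7 and Appendix b)
- SD of 9 hours (Section 7)

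Assumptions, not in the documents: every one of the 12 is later rated by their own interviewer, and knowledge of the arm shifts rated hours by δ between arms in those participants. The range for δ is 1 to 4 hours, with 2 hours as the central value.

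Share exposed = 12/100 = 12% (6/50 in each arm).

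Shift in the estimated difference = 0.12 × δ:

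| Assumed δ (hours) | Shift in estimate (hours) | Share of the 4-hour minimum benefit |
|---|---|---|
| 1 | 0.12 × 1 = 0.12 | 0.12/4 = 3% |
| 2 | 0.12 × 2 = 0.24 | 0.24/4 = 6% |
| 4 | 0.12 × 4 = 0.48 | 0.48/4 = 12% |

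For scale, the standard error of a difference in means at 50 per arm is 9 × √(2/50) = 1.8 hours. The central shift is 0.24/1.8 = 13% of one standard error. If the 12 participants were part of a trial of about 300, the size Section 7 anticipates, the central shift would be 12/300 × 2 = 0.08 hours, or 2% of 4 hours.

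**The case against.** The strongest reply is that the two sections can be read together. There are two centres, and Section 13 has senior RAs recruited in each. An RA from the other centre could count as a researcher from another service, and a rating is compromised only if the interviewer later assesses that participant or passes on what was learned. This part stands: the protocol leaves a gap in its safeguards and does not describe an actual breach. But Section 11 mentions no cross-centre arrangement, and Section 3's condition does not separate interviewing from rating. The reconciliation has to be supplied by the reader.

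Three stronger readings are tempting and are not supported.

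- A reader might infer that the single-blind claim fails for every interviewed participant. That would require each interviewer to rate their own interviewees, which is nowhere stated.
- A reader might add the 16 Phase 2 interviews and count 28 of 100 participants as exposed, with a shift of 0.56 hours at δ = 2. Phase 2 names no interviewer, so Section 3's rule is the only one that applies and nothing contradicts it. Nothing prevents the same person from being interviewed in both phases, and a 9-month interview held after that visit's rating could affect only the 15-month rating.
- A reader might note that 12 is 30% of the 40 participants sought by the end of year 1 and fear for the progression decision. That decision rests on recruitment, completeness of data, therapy delivery, acceptability and the need for protocol changes, not on an estimated treatment effect.

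It is also fair to say that assessor blinding is not the only safeguard. Section 4 allows time in work and education to be checked against case worker report. Section 3 has assessors guess the allocation at each assessment, which could help reveal a loss of blinding but would not undo it. Finally, Section 11 does not say that RAs select the interviewees or hold the list by arm, so it cannot be claimed that they learn allocation through sampling.

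**Conclusion.** The point holds for Phase 1. Sections 3 and 11 name different interviewers, the Section 11 choice is the staff group that must stay blind, and neither section prevents the same person from interviewing and then rating a participant. Up to about 12 of 100 participants are exposed at 9 and 15 months, and possibly at 3 months.

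The numerical effect is small: about 0.24 hours under the 2-hour assumption. This treats all 12 as rated by their own interviewer, so for a given shift it is an upper limit; the size of the shift is itself assumed. The case for acting rests less on this figure than on an internal conflict about blinding that is cheap to remove before the interviews start.

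**What to change.** 1. In Section 11, Phase 1, replace the reference to RAs with a researcher who performs no outcome assessment on that participant, for example the university researcher foreseen in Section 3 or the other centre's RA.
2. Add the same condition to the Blinding paragraph in Section 3, alongside independence from the clinical team, so that it covers both phases.
3. State that recordings, transcripts and the sampling list by arm are kept from the raters until that participant's final assessment.

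The cost is a few sentences of protocol text. No extra staff should be needed, because Section 3 already foresees a separate interviewer. The small downside is scheduling interviews across sites.
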